9.2 Source Documents

The Investigator must maintain source documents for each study participant in the study, consisting of case and visit notes (hospital or clinic medical records) containing demographic and medical information, radiological, and the results of any other tests or assessments. All information in electronic/paper Case Report forms must be traceable to these source documents. The Investigator must also keep the original informed consent form signed by the study participant (a signed copy is given to the study participant). The Investigator must give the monitor access to all relevant source documents to confirm their consistency with the eCRF entries. As per ISO14155:2020 the study sites must adhere to all standards, adherence to the inclusion/exclusion criteria, documentation of SAEs, and the recording of relevant study data.

9.3 Case Report Forms

The Sponsor will provide the Case Report Forms (in paper and/or electronic form) to the site to enable collection of the study data. The Investigator is responsible for ensuring that all sections of each paper or eCRF are completed promptly and correctly and that entries can be verified against any source data. Principal Investigator should routinely review the case report forms for completeness and accuracy as well as any evidence which may be indicative of patient risk. When any discrepancies are noted, they will be resolved with the Investigator and/or individual designated by the Investigator. When the data are incomplete, attempts will be made to obtain the data whenever possible. Study monitors will perform source document verification on site and remotely to identify inconsistencies between the eCRFs and source documents. Discrepancies will be resolved in accordance with the principles of ISO14155:2020.

9.4 Archiving of Study Documents

All study related correspondence, study participant records, consent forms, study participant privacy documentation, records of the distribution and use of all investigational device, and copies of case report forms should be maintained on site files. The sponsor and principal investigator shall maintain the clinical investigation documents as required by the applicable regulatory requirement(s). The Investigator follows the principles outlined in the Clinical Study Agreement (or equivalent) for responsible archiving.

The study data will be stored for 15 years. After that the data will be archived electronically on a secure server for at least 10 years after the last product has been distributed.

10.0 STATISTICAL CONSIDERATIONS

10.1 Statistical Methods and Data Analysis

The following describes the statistical analyses foreseen at the time of study planning. Detailed statistical methods will be described in a separate Statistical Analysis Plan (SAP).

Statistical analyses will be performed when data has been collected for the study population at 2 years, 5 years, and 10 years follow-up.

Descriptive statistics will be provided in summary tables according to the type of variable summarised:

- survivorship will be calculated as Kaplan-Meier analysis with 95% confidence interval.
- quantitative variables will be summarized by using n (sample size), arithmetic mean, standard deviation (SD), median, minimum, and maximum, comparing between follow-ups and baseline values (where applicable).
- categorical variables will be summarized by using frequency count and percent distribution. Additional analysis may include comparisons of interest across demographic and baseline characteristics.

The analyses will include:

Analysis of primary endpoint:

- Percent change and absolute improvement of OHS will be reported at each follow-up visit compared to pre-op and previous visit(s) using a repeated-measures t-test.

Analysis of secondary endpoints:

- The survival of the devices will be expressed as crude revision rates and 95% confidence intervals and include listing of details of revision procedures (reason, time to revision, components revised).
- Hip-/ procedure-/ device- related adverse events will be listed and summarized based on the different mechanisms of classification, such as type of event, timing (operative/post-operative), seriousness and relation with the study devices.
- Postoperative HHS compared to pre-op baseline and previous visits. Percent change and absolute improvement will be reported for total scores and/or sub-scores as appropriate.
- Postoperative EQ-5D-5L compared to pre-op baseline and previous visits. Percent change and absolute improvement will be reported for total scores and/or sub-scores (EQ-VAS) as appropriate.
- Patient's satisfaction with the results of the surgery and any change to previous visit.

 The rates and extent of any radiolucent lines, osteolysis and rates of implant loosening will be reported at specified follow-up time points, as assessed by available radiographs.

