In addition, Corin is conducting an ongoing long-term PMCF study (Study Ref: 1302-T-HIPLTO-RM) in France with the purpose to collect clinical and functional scores, PROMs, and radiographic data after THR surgeries with Corin hip prostheses including dual mobility procedures with MobiliT cup and the standard polyethylene (PE) insert. A total of 1100 primary THR surgeries with the cementless MobiliT cup have been performed between June 2014 and November 2021. Most of patients are female (68.6%) with an average age at the time of surgery of 77.6 ± 8.2 years old and a BMI of 27.5 \pm 5.2. The average HHS increased from 41.1 \pm 17.7 before surgery to 93.7 \pm 8.8 at 2.5 years with 93% of the study population showing satisfactory (HHS≥80) results at 2.5 years. A substantial increase was already observed after 3 months from surgery providing excellent recovery post-surgery. The OHS improved considerably from 15.4 \pm 8.2 before surgery to 45.3 \pm 5.0 at 2.5 years. Ongoing results show that the patient's satisfaction has been achieved with overall satisfaction average score of 96.5 ± 9.0 at 2.5 years. The EQ-5D VAS scored from an average of 59.4 ± 18.4 preoperatively to 82.7 ± 15.0 at 2.5 years confirming an improved status of health. A good postoperative restoration of biomechanical parameters was observed with X-rays demonstrating good implant stability and cup integration with average cup inclination of 44.7 ± 4.5 degrees at 2.5 years. No radiolucent lines or osteolysis have been reported. Two (0.2%) cases of heterotopic ossification categorised as Brooker class III at 3 months and 2 (0.4%) at 2.5 years. A total of 62 (5.6%) postoperative complications have been reported of which 16 (1.5%) led to a revision surgery. No revisions due to dislocation were reported. Kaplan Meier Survival rate is 95.89% (95% CI: 90.08%, 98.33%) at 5 years. Ongoing results at 2.5 years seem to confirm previous published data with a significant increase in joint functionality and PROMs data. The ECiMa insert compatible with the MobiliT Cup has been added to the above-mentioned study in mid-2022 and data is being collected.

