4.0 STUDY ENDPOINTS

4.1 Primary Endpoint

Improvement of Oxford Hip Score (OHS) from baseline (preop) to 2 years after surgery.

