7.2 Clinical Assessment and Patient Reported Outcome Measures (PROMs)

The clinical assessment is performed before surgery, at 3 months, 1 year, 2, 5, 7 and 10 years after the surgery. Preoperative assessment is used as baseline values for score improvement.

Harris Hip Score

The Harris Hip Score (HHS) is a disease-specific scoring system originally intended as outcome score after arthroplasty surgeries that include the domains of function, pain, motion, and deformity 16. The HHS is considered a clinical outcome measure. The maximum score of the absolute HHS is 100 points. Pain domain contributes 44 points, function 47, ROM 5 and absence of deformity 4 points. Function is subdivided into gait and activities of daily living. Calculation of the ROM score includes splitting the motion into categories based on utility and then multiplying the degrees of motion with a given index factor. The index scores are then added and multiplied by a factor of 0.05 to obtain the final ROM score. The ROMs of the affected hip/joint will be measured with a standard goniometer.

Oxford Hip Score

Oxford Hip Score (OHS) is a patient-centred questionnaire that is designed to assess functional ability and pain from the patient's perspective. It is a short, twelve-item questionnaire developed for completion by patients undergoing THA and is extensively referenced in the Orthopaedic literature. The OHS has been demonstrated to be highly sensitive to change in patients undergoing primary THA.¹⁷ Each of the 12 questions on the Oxford hip score presents a score decreasing as the reported symptoms increase (ie. become worse). All questions are laid out with response categories denoting least (or no) symptoms being to the left of the page (scoring 4) and those representing greatest severity lying on the right-hand side (scoring 0). This method, when summed, produces overall scores running from 0 to 48 with 48 being the best outcome.

EQ-5D-5L

The EQ-5D-5L essentially consists of 2 pages: the EQ-5D descriptive system and the EQ visual analogue scale (EQ VAS).

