The descriptive system comprises five dimensions: mobility, self-care, usual activities, pain/discomfort and anxiety/depression. Each dimension has 5 levels: no problems, slight problems, moderate problems, severe problems and extreme problems. The patient is asked to indicate his/her health state by ticking the box next to the most appropriate statement in each of the five dimensions. This decision results in a 1-digit number that expresses the level selected for

that dimension. The digits for the five dimensions can be combined into a 5-digit number that describes the patient's health state.

The EQ VAS records the patient's self-rated health on a vertical visual analogue scale from 0-100, where the endpoints are labelled 'The best health you can imagine' and 'The worst health you can imagine', it is requested for the patient to simply mark an X on the scale to indicate today's health and to write the number marked on the scale in the box. The VAS can be used as a quantitative measure of health outcome that reflect the patient's own judgement.

Subject's satisfaction 4-point Likert-type scale

The overall satisfaction of the patients with the result of the surgery will be scored on a 4-point Likert-type scale with response categories consisting of very satisfied (100 points), somewhat satisfied (75 points), somewhat dissatisfied (50 points) and very dissatisfied (25 points)¹⁸. The satisfaction scale will be completed by the participant postoperatively and the first one will represent the baseline for the following visits.

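### The primary analysis gives percent change of the Oxford Hip Score equal standing with absolute change; computed per hip, its mean would be inflated and unstable, and the sample size rests on absolute points only

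*Protocol*

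**What the plan says.** Section 4.1 defines the primary endpoint as "Improvement of Oxford Hip Score (OHS) from baseline (preop) to 2 years after surgery" and does not say whether improvement is in points or in percent. Section 10.1, under the analysis of the primary endpoint, names both: "Percent change and absolute improvement of OHS will be reported at each follow-up visit", "compared to pre-op and previous visit(s) using a repeated-measures t-test". The statistical methods row of the synopsis says the same. Neither statistic is designated as the primary one, and no formula for percent change is given.

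Section 10.2 bases the 100 hips on a mean difference of 22.6 OHS points (SD 9.8), two-sided alpha 0.05 and power above 0.90. Percent change has no part in it.

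Section 7.2 says that the OHS "produces overall scores running from 0 to 48 with 48 being the best outcome". Section 3.1 gives results from the sponsor's ongoing French study of the same cup with the standard polyethylene insert: "The OHS improved considerably from 15.4 \pm 8.2 before surgery to 45.3 \pm 5.0 at 2.5 years".

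For the EQ-5D-5L, a secondary endpoint, section 10.1 says: "Percent change and absolute improvement will be reported for total scores and/or sub-scores (EQ-VAS) as appropriate". Section 7.2 describes a visual analogue scale from 0 to 100 and a health-state code: "The digits for the five dimensions can be combined into a 5-digit number that describes" the patient's state. It describes no index or total score.

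**The concern.** Percent change from baseline divides each hip's gain by its own starting score. On a scale whose floor is 0, with a low and widely spread starting score, the divisor is sometimes very small and can be zero. A few hips with poor baselines can then supply much of the mean. The measure can also rank results against clinical sense: a hip going from 2 to 20 scores (20 − 2)/2 = +900%, while one going from 20 to the maximum of 48 scores (48 − 20)/20 = +140%.

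What is at stake is the reported size of effect. The results feed the annual clinical evaluation, the MDR submission and publications (sections 3.4 and 10.1, and the synopsis). With two statistics sharing primary status, either can become the headline, and the less stable one gives the larger number.

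**Working it through.** **1. The plan's own power figure.** Inputs from section 10.2: mean change 22.6, SD 9.8, n = 100, two-sided alpha 0.05.
- Noncentrality = 22.6/9.8 × √100 = 23.1 on 99 degrees of freedom; power is above 0.999. The stated figure of above 0.90 is met, on the absolute scale.
- Five hips would already give power of 0.96.

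**2. How low baselines can fall.** Inputs from section 3.1: mean 15.4, SD 8.2.
- Zero lies 15.4/8.2 = 1.88 SD below the mean.
- The protocol gives only the mean and SD, so the shape is an assumption. Two were used: a beta-binomial on 0 to 48 matched to 15.4/8.2, and a normal with those parameters truncated and rounded to 0 to 48.
- Share of hips at exactly 0: 0.43% (beta-binomial) to 0.86% (truncated normal).
- Chance of at least one undefined value in 100 hips: 1 − (1 − 0.0043)^100 = 35%, to 1 − (1 − 0.0086)^100 = 58%.
- Share of hips with baseline 1 to 5: about 8 to 10%.

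**3. What the divisor does.** The planned gain of 22.6 points is 22.6/1 = 2260% from a baseline of 1, 22.6/5 = 452% from 5, and 22.6/15 = 151% from 15.

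**4. Simulation.** 10,000 studies of 100 hips each; baseline as in step 2; follow-up a beta-binomial matched to 45.3/5.0; latent correlation 0 or 0.5; zero baselines dropped.

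| Quantity | Per-hip percent change | Absolute change |
|---|---|---|
| Mean | 313 to 362% | 29.4 to 29.9 points |
| SD | 450 to 534 | 7.4 to 9.6 points |
| Median | 187 to 212% | not needed |
| Share of total from the 5 largest values | 27 to 31% | 7 to 8% |
| Share of total from baselines 1 to 5 | 37 to 43% | not computed |
| Paired t statistic | 6 to 8 | 31 to 40 |

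- Across the four scenarios, the 95% ranges of the study mean percent change span about 238% to 487%.
- The half-width of a t-based 95% CI for that mean at n = 100 is 1.984 × 450/10 = 89 to 1.984 × 534/10 = 106 percentage points.
- A repeat of the simulation gave means of about 335 to 367% (SD about 545). The rounded ranges used here, 310 to 370% with SD 450 to 550, cover both runs.
- The truncated normal does not return its inputs exactly (baseline mean 15.9, SD 7.7). The beta-binomial does, and gives the higher means.

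**5. Change in means.** (45.3 − 15.4)/15.4 = 29.9/15.4 = 194%. This needs no assumption about shape and is unaffected by single low baselines.

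**6. EQ-5D-5L code.** If the five digits were treated as a number, 21111 to 11111 would be −10000/21111 = −47%, and 11112 to 11111 would be −1/11112 = −0.01%. Each is one level on one dimension, so the code cannot carry a percent change.

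**The case against.** The strongest reply is that the protocol never says the percentage is computed per hip. It could be the change in means over the baseline mean, for which the distortion disappears. The t-test clause can also be read as applying to the visit scores, which fits a sample size in points, and the synopsis calls the analysis descriptive. Formulas and zero-baseline rules are ordinary SAP content. This stands in part: the per-hip reading is an inference, though the natural one beside a paired test. But the choice of percent change as a co-equal primary statistic is made in the protocol, and the two readings differ by more than 100 percentage points.

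Several stronger readings are tempting and should be resisted.
- A reader might infer that OHS starts near zero. Only the scale floor is 0; the expected mean is 15.4, and zeros should be under 1% of hips. A figure of about 3.5% arises only if a normal curve's whole lower tail is piled on zero.
- A reader might infer that the test fails or that improvement could be wrongly claimed. Even for percent change the t statistic is about 6 to 8.
- A reader might infer that hips would vanish unnoticed or that skew would be hidden. Section 10.1 requires n, median, minimum and maximum, and absolute improvement stands in the same sentence.
- Fracture is an indication for the cup, but the documents give no figure for its effect on baseline OHS.
- The protocol does not say that percent change will be taken of the five-digit EQ-5D-5L code. It names EQ-VAS and adds a qualifier, and the SAP may settle the rest.
- The argument does not carry over with equal force to the Harris Hip Score or EQ VAS. In section 3.1 zero lies 41.1/17.7 = 2.3 SD and 59.4/18.4 = 3.2 SD below their baseline means.

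**Conclusion.** The point holds as a poorly chosen stated statistic, not as a threat to the study's conclusion. Percent change of OHS shares primary status with absolute change, although only absolute change is supported by the sample size. Computed per hip, its mean would exceed the change in means by roughly 310 − 194 = 116 to 370 − 194 = 176 percentage points, with close to 40% of the total coming from about a tenth of the hips.

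This rests on three assumptions: that the calculation is per hip, that baselines resemble those in the sponsor's French study, and that their distribution is close to the shapes tried. The direction does not depend on the exact shape; the size does. Power, sample size and the finding of improvement are unaffected. The EQ-5D-5L matter is a separate, smaller wording point on a secondary endpoint.

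**What to change.** In section 10.1 and the synopsis, name absolute change in OHS from pre-op to 2 years, with a 95% CI, as the sole primary statistic, and remove percent change from the t-test. If a relative figure is kept, report it descriptively as the change in group means divided by the baseline mean, or as the median of the per-hip values with a stated rule for baseline 0.

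For the EQ-5D-5L, state that change is reported for EQ VAS, or for an index with a named value set, and never for the five-digit code.

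Cost: wording only, with the ethics approval that section 11.4 requires for any amendment. The 100 hips stand, and power on absolute change stays above 0.999. The downside for the sponsor is a smaller headline percentage, about 194% in place of 310 to 370% on the section 3.1 figures.

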- The survival of the devices will be reported as crude revision rates and 95% confidence intervals, and include listing of details of revision procedures (reason, time to revision, components revised).
- Hip-/ procedure-/ device- related adverse events will be listed and summarized based on the different mechanisms of classification, such as type of event, timing (operative/post-operative), seriousness and relation with the study devices.
- Postoperative HHS compared to pre-op baseline and previous visits.
 Percent change and absolute improvement will be reported for total scores and/or sub-scores as appropriate.
- Postoperative EQ-5D-5L compared to pre-op baseline and previous visits. Percent change and absolute improvement will be reported for total scores and/or sub-scores (EQ-VAS) as appropriate.
- Patient's satisfaction with the results of the surgery and any change to previous visit.
- Rate and extent of any radiolucent lines, osteolysis and rates of implant loosening will be reported at specified follow-up time points, as assessed by available radiographs.

Statistical methods, summaries and analyses may differ for ad-hoc interim reports depending on the requirements for which the report is being prepared. The statistical methods will be described further in the study protocol or in a separate Statistical analysis plan (SAP).

Sample size: A minimum of 100 hips will be enrolled into the study, which will be sufficient to demonstrate an OHS change over time with an alpha of 0.5 and a power >0.9.

[figure not shown]
Statistical Methods and Sample Size

Data Quality Control	Corin will ensure the study is conducted in accordance with the CSP and all applicable requirements through centralised and on-site monitoring of data and source documents.
Standards & Ethical Considerations	EC approval EN ISO 14155 Guidelines ICH/GCP Declaration of Helsinki (July 2018) GDPR data security compliance The study will be registered in a publicly accessible database before recruitment of the first subject (e.g. Australian New Zealand Clinical Trials Registry (ANZCTR).
Data Quality Control Methods	Site qualification visits and regular data monitoring (remote and on-site)

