6.0 STUDY POPULATION

Participants will be selected for recruitment into the study from the general population of patients requiring a primary total hip arthroplasty surgery with a dual mobility construct and considered suitable for the cementless MobiliT cup with ECiMa insert with Paragon or TaperFit stem. Participants who do not meet the inclusion criteria or meet any exclusion criteria are excluded from the study participation. Bilateral participants will be included, and each hip will be assigned a specific study ID and the patient will complete separate questionnaires for each treated hip.

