8.3 Postoperative Withdrawal

After the surgery, the participant may voluntarily revoke consent and withdraw from the study at any time without reason. Participants may be involuntarily exited from the study for failure to comply with the study protocol, failure to attend follow-up visits or for any clinical condition, if the Investigator deems it necessary.

In all cases, the Investigator should record the withdrawal indicating the date, the reason (if available) and the last date of follow-up available. All data obtained up to consent withdrawal will be included in the analysis.

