10.2 Sample Size

A minimum of 100 hips will be enrolled into the study according to the selection criteria. Based on a repeated-measures t-test, and assuming a mean difference of 22.6 OHS score points (SD 9.8) from pre-operative to 2 years post-operative²⁰, this sample size will be sufficient to demonstrate a two-tailed effect with an alpha of 0.05 and a power >0.90.

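### The hip-level paired t-test for the primary OHS change ignores bilateral patients and uses only hips with both scores: a modest error that is cheap to correct

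*Protocol*

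**What the plan says.** Section 10.1, like the statistical methods in the synopsis, reports percent and absolute OHS change at each follow-up visit, "compared to pre-op and previous visit(s) using a repeated-measures t-test". Section 10.2 sizes the study on the same test and counts hips: "A minimum of 100 hips will be enrolled into the study according to the selection criteria", "assuming a mean difference of 22.6 OHS score points (SD 9.8) from pre-operative to 2 years post-operative", for a "two-tailed effect with an alpha of 0.05 and a power >0.90".

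Section 6.0 states: "Bilateral participants will be included, and each hip will be assigned a specific study ID". Such a patient fills in separate questionnaires for each treated hip. Nothing in the protocol mentions correlation between two hips of one patient.

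On incomplete follow-up, section 8.3 says: "All data obtained up to consent withdrawal will be included in the analysis". Section 8.4 ends follow-up at revision or death and keeps the data collected up to a revision. Table 1 schedules OHS pre-op and at 3 months and 1, 2, 5, 7 and 10 years. Section 10.1 leaves detailed methods to a separate SAP, which is not available here.

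**The concern.** A paired t-test deals with the pairing of pre-op and follow-up scores within a hip. It then takes the hips themselves as independent. Two hips of one person share comorbidity, general recovery and response style, so their changes are likely to be positively correlated. The test then overstates the amount of information and returns a standard error and p-value that are too small.

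The same assumption underlies the 95% intervals that the protocol does promise, for Kaplan-Meier survival and crude revision rates. It also affects EQ-5D-5L, which section 7.2 describes as the patient's own health state: with one questionnaire per hip, a bilateral patient enters as two independent people.

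Separately, the pre-op to 2-year comparison can use only hips with both scores. A hip lost after 1 year adds nothing to the primary estimate, although its 3-month and 1-year OHS were collected and carry information about its likely 2-year result. If hips doing poorly are more often missing, the mean improvement among completers is too favourable.

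**Working it through.** **The plan's own figure.** Inputs from section 10.2: mean change 22.6, SD 9.8 (read as the SD of the change), 100 hips, two-sided alpha 0.05. The noncentrality is 22.6/9.8 × √100 = 23.1, so power is about 1.00 and the stated bound of >0.90 is met. Five hips would already give 0.964 (four give 0.853). The synopsis prints alpha as 0.5 ("sufficient to demonstrate an OHS change over time with an alpha of 0.5 and a power >0.9"); that is a separate inconsistency and plays no part here.

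**Precision with independent hips.** SE = 9.8/√100 = 0.98. The normal 95% half-width is 1.96 × 0.98 = 1.92 points (1.94 with the t quantile).

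**Clustering.** The bilateral share and the correlation ρ of change between a patient's two hips are assumptions, because the protocol gives neither. With m hips per patient, design effect = 1 + (Σm²/Σm − 1) × ρ. This equals 1 + b × ρ, where b is the share of hips from bilateral patients. For 20 bilateral and 60 unilateral patients, Σm²/Σm = (20 × 4 + 60)/100 = 1.4, so with ρ = 0.5 the design effect is 1 + 0.4 × 0.5 = 1.20. True half-width = 1.92 × √(design effect). Coverage of a nominal 95% interval = 2Φ(1.96/√(design effect)) − 1.

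| Bilateral patients (100 hips) | b | ρ | Design effect | True half-width | Increase | Coverage |
|---|---|---|---|---|---|---|
| 10 | 0.2 | 0.3 | 1.06 | 1.98 | 0.06 | 94.3% |
| 20 | 0.4 | 0.5 | 1.20 | 2.10 | 0.18 | 92.6% |
| 30 | 0.6 | 0.7 | 1.42 | 2.29 | 0.37 | 90.0% |

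In the middle row the t-test's SE is too small by 1 − 1/√1.20 = 8.7%, and the effective sample is 100/1.20 = 83 hips. With fewer bilateral patients the effect shrinks: b = 0.1 and ρ = 0.5 give a design effect of 1.05 and a half-width of 1.97. A simulation of the naive interval at b = 0.2, ρ = 0.5 gave 94.0% coverage, against 93.8% from the formula; a patient-clustered SE gave 94.9%.

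**Does it touch the conclusion?** No. In the bottom row the SE is 0.98 × √1.42 = 1.17, and 22.6/1.17 is about 19 standard errors. Even with 50 bilateral patients and ρ = 1 (effective n = 50), power stays above 0.999.

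**Missing 2-year scores.** This is an illustration under assumptions: 100 hips, b = 0.2, ρ = 0.5, a correlation of 0.7 between 1-year and 2-year change, poorer results more often missing (log-odds 1 per SD), and 3000 runs. The missing rates are nominal. The comparator is a regression-based likelihood estimate using the 1-year score, as a stand-in for the mixed model; a full mixed model was not fitted. Entries are bias in OHS points at 10 / 20 / 30% missing.

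| Missingness depends on | Paired t-test | Likelihood estimate |
|---|---|---|
| observed 1-year change | +0.80 / +1.43 / +1.91 | −0.01 / +0.02 / 0.00 |
| unseen 2-year change | +1.19 / +2.02 / +2.68 | +0.65 / +1.11 / +1.46 |

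Using the earlier scores removes the bias in the first case and roughly halves it in the second.

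**The case against.** Several points on the other side are sound.

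- A reader might infer that the t-test contradicts section 8.3. It does not: section 10.1 compares every visit with pre-op, so a hip withdrawn after 1 year still enters the 3-month and 1-year comparisons. Section 8.3 does not promise that such a hip informs the 2-year estimate. What stands is that earlier scores are left unused where they would help the primary endpoint.
- A reader might infer that a mixed model cures the missing-data problem. It does so only under missing at random. For revised hips, whose follow-up stops by design, and for patients who die, it would implicitly estimate a 2-year score as if they had continued unrevised or alive.
- A reader might infer that planned OHS confidence intervals are too narrow. The protocol names 95% CIs only for survival and revision rates. For OHS, what is affected is the standard error and p-value of the named test.
- The study is called descriptive, and the clustering effect is small in OHS points. That limits the weight of the point. But the same synopsis names a t-test, an alpha and a power, and section 3.4 sends the results to regulatory evaluation and publication, where the size and precision of the improvement are what is read.
- Clustering and missing-data detail commonly belong in the SAP. That would answer silence. Here the protocol names the test and sizes the study on it, so an SAP using a different method would depart from the protocol.

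**Conclusion.** The point holds in limited form. The named hip-level t-test does not fit a sample that may contain both hips of one patient: its standard error and p-value are too small whenever bilateral patients are enrolled and their two changes are positively correlated. Under the assumed ranges the understatement is 0.06-0.37 points on a half-width of 1.92; with no bilateral patients it is nil. The complete-pair restriction may matter more. At 20-30% missing, the simulated bias of 1.4-2.7 points is comparable with or larger than the half-width, but it depends wholly on assumed missing rates and mechanisms. No size was computed for the effect on survival intervals or EQ-5D-5L; the reasoning there is structural. The documents do not support any claim that 100 hips are too few, that the stated power fails, or that the conclusion of improvement is in doubt.

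**What to change.** In the synopsis and section 10.1, replace the repeated-measures t-test by a mixed model for repeated measures on OHS:

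- Use visit as a factor, with patient and hip-within-patient effects. Let the patient effect differ by visit, or cluster the standard errors by patient: a patient effect that is constant over visits cancels out of a change and would leave the problem in place.
- Prespecify the covariance structure.
- Fit the model at each analysis to the visits available by then; for the primary analysis these are pre-op, 3 months, 1 year and 2 years.
- Report the 2-year change with its 95% CI.

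State that the model is valid under missing at random, and that it reduces but does not remove bias if missingness depends on the unseen 2-year score. Say how hips revised, and patients who die, before 2 years are handled in the analysis.

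Use patient-clustered variance for the 95% CIs of Kaplan-Meier survival and crude revision rates. Account for patient clustering in EQ-5D-5L and EQ VAS as well. Clustering is safer than one record per patient, because two hips operated on at different dates have different baselines and visit schedules.

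The cost is a little more analysis work and slightly wider intervals. No extra hips or data are needed.
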